OGTT or a fasting glucose lab test) to provide the results of either of these tests, as well as a documented weight. The weight can either be self-reported or from their health care provider at 12 months (+/- 3 months postpartum). Participants will also be asked to complete a questionnaire at 6 weeks to 3 months, and 6, 9, and 12 months postpartum.

Group 3: (see Table 3) On-line nutrition and physical activity class and block blood glucose testing— This group will take part in the above-mentioned standard care and on-line nutrition and physical activity classes at 6 weeks to 3 and 9 months. In addition, participants in this group will take blood glucose levels with provided meters and test strips four times a day for 4 consecutive days once a month starting at 3 months postpartum and concluding at 9 months postpartum to check patterns of glucose before breakfast and 2 hours after each meal. Women will also be asked to self-report their weight at these times. For those women who choose to have diabetes screening at 12 months +/- 3 months through either a 75 gram 2 hour OGTT or a fasting glucose taken at a laboratory, we will request the test results at that time point. We will also collect the study participants weight from either self-report or their health care provider at 12 months postpartum. Each participant will be asked to complete a questionnaire at 6 weeks to 3months, and 6, 9, and 12 months postpartum.

OUTCOMES:

1. Adherence to diabetes screening using the 75 gram 2 hour OGTT or fasting blood glucose at 12 months (+/- 3 months)
2. Lab results from the fasting glucose test or results from a 75 gram 2 hour OGTT at 12 months among women who choose to take the diabetes screening test.
3. Postpartum weight loss (target 7% less than the pre-pregnancy weight for overweight/obese women and back to pre-pregnancy weight for normal BMI women). This will be based on medical record information on pre-pregnancy weight and self-reported or health-care provider reported weight at 12 months.

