4. Determine to what extent barriers to health impact adherence rates to post partum screening and weight loss targets through a web-based questionnaire collected on the 6 weeks to 3 months, 6, 9, and 12 month questionnaires. These questionnaires will assess whether: lack of self care, perception of high infant care giving needs, fear of diabetes diagnosis and postpartum depressive symptoms, difficulty accessing medical care, dissatisfaction with medical care or primary care physician not recommending screening are associated with poorer adherence to diabetes screening guidelines and weight loss goals.

Study aims are:

1. Determine the extent to which women who receive a postpartum group nutrition intervention and/or block blood glucose testing return for a 12 month (+/- 3 months) follow-up screening for diabetes with either a fasting blood glucose test or a 75 gram 2 hour OGTT compared to women who receive standard care. *We hypothesize that women in Group 3 will be the most likely to return for screening at their 12 month follow-up (+/-3 months).*
2. Determine the extent to which women who choose to have diabetes screening conducted at 12 months postpartum and who receive a postpartum group nutrition counseling intervention and/or block blood glucose testing are more likely to have fasting glucose or a 75 gram 2 hour OGTT results within normal range at 12 months (+/- 3months) compared to women who receive standard care.
3. Determine the extent to which women who receive a postpartum on-line nutrition and physical activity counseling intervention and/or block blood glucose testing will meet postpartum weight goals at 12 months postpartum (i.e. more likely to lose 7% of their pre-pregnancy body weight if

Approved by

JDC/ CHS

CHS#2012-16

MM

Date: 03/10/2014

they have a BMI ≥ 25 or return to their pre-pregnancy weight if their BMI < 25) compared to women who receive standard care.

2 STUDY DESIGN:

METHODS:

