Study Population: During the 3rd trimester of pregnancy and up until 3 months postpartum, we will recruit a total of n=30 women (10 women in each group) with GDM or a recent history of GDM, who are seen by clinical staff at the Joslin Diabetes Center/Beth Israel Deaconess Medical Center's (JDC/BIDMC) Diabetes and Pregnancy Program. Study participants would have delivered between June 1, 2012 and May 31, 2016. Recruitment for the study will occur at Joslin Diabetes Center after the second visit for GDM in the Diabetes and Pregnancy Program. A research assistant will provide information about the study, review an informed consent form and offer participation in the study. Potential subjects will be advised that participation is voluntary and should they agree to participate in the study, they will be randomized to 1 of three intervention groups to which they will not have a choice of group assignment.

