3. INCLUSION / EXCLUSION CRITERIA

Inclusion criteria:

1. Gestational Diabetes
2. Age between 21 and 45 years
3. Preconception BMI 19-40
4. Seen for at least 2 visits in the Diabetes in Pregnancy Program during their pregnancy
5. Singleton pregnancy

Exclusion criteria

1. Preexisting diabetes or diabetes diagnosed at the 6 week 75 gram 2 hour OGTT

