4. DATA ANALYSIS / SUBJECT SELECTION

For aim 1, we will calculate the proportion of women who received postpartum diabetes screening in each group using intention-to-treat analysis. We will calculate the association between the interventions versus standard care by calculating chi-square and p-values to assess statistical significance. For aim 2, we will evaluate the association between our intervention and continuous blood glucose levels among women who received the 12-month 75 gram 2 hour OGTT or glucose. We will use ANOVA to calculate F-statistics and p-values to determine whether the intervention was associated with improved blood glucose levels compared to the standard care. Similarly, for aim 3, we will evaluate the association between our intervention and continuous weight measurements using ANOVA. As a secondary hypothesis, we will use multivariable binomial regression to evaluate the association between age, race/ethnicity, sociodemographic factors, self-care, perceived infant care giving needs, fear of diabetes, and access/satisfaction with medical care, and adherence to postpartum diabetes screening at 12 months. We will calculate risk ratios and 95% confidence intervals, adjusting for potential confounders, including sociodemographic factors. We will primarily assess these results for directionality. We will use SAS version 9.2 (Cary, NC) for all analyses.

The proposed project is a pilot study. Therefore, we anticipate having limited power to detect statistically significant results. However, the direction and magnitude of the associations will provide necessary data required for a larger research study to further improve adherence to diabetes screening guidelines after GDM, as well as potentially improve blood glucose results for women in the first year postpartum and reduce weight retention. As such, this study is clinically significant, given that it may provide insight into how to improve adherence to follow-up diabetes screening and subsequent prevention or delayed diabetes diagnosis. This data analysis will be performed by [name] and [name].

Local Interim Data Analysis/Data Monitoring Plan

Approved by

JDC/ CHS

CHS#2012-16

AP

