Women with gestational diabetes who have seen a Joslin Diabetes Center Diabetes and Pregnancy Program provider at least two times during their pregnancy between June 2012 and May 2016 will either be approached during a scheduled clinic visit or contacted by telephone by their provider (also co-investigator) or the Research Assistant. If interested in learning more about the study, the CITI-certified, IRB-approved Research Assistant will be introduced to the woman and will take the woman into a private room where the Research Assistant will describe the study in further detail. The Research Assistant will meet with the potential study candidate, inform the woman about the purpose of the study, as well as provide a brief description of the study design and outcome measures. Women will also be informed of possible benefits and risks of the study. At this time, the Research Assistant will obtain verbal consent to conduct the screening questionnaire to determine a woman's eligibility. If a woman is eligible, she will receive a study participant letter further describing the purpose of the study, as well as the informed consent form to which CITI-certified, IRB-approved Research Assistant will briefly review with the potential study participant. Each woman will be given time to review it before signing. During the review, if the eligible subject has any questions regarding the study, she can raise them with the CITI-certified, IRB-approved Research Assistant or the Principal Investigator. If the eligible subject wishes to bring the consent form home for review, she will be allowed to do so and will be asked to bring the form back on her next visit to Joslin for signing after further clarification of any queries. As mentioned above, the study participant will then receive a copy of the signed informed consent and will be enrolled into the study. At this time, we will use block randomization, using a random number generator to assign women into one of the three study groups. Block randomization will ensure an equal distribution of women into each arm. Women will not have the option of choosing their assignment. They will also not be blind to which group they have been assigned to for participation in the study.

Approved by
JDC/ CHS
CHS#2012-16

9. RIGHTS AND PRIVACY:

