The data for each subject will be extracted from her medical record data in Joslin Diabetes Center for statistical analysis by [name]. After abstracting the data, it will be merged via the key with the personal identifiers dataset housed on [name] computer (PI) with questionnaire data by [name] and the Research Assistant. Once this merge takes place, personal identifiers will be removed and only the unique study ID will remain attached to this information. As described in Section 6, the key to the code, linking the subject's personal information to the subject will be kept in a locked file in Joslin Diabetes Center. Only [name] (PI) and [name] RD will have access to the key to the code.

Only the following data from medical records will be sent to the co-investigators for data analysis:

- Height
- Weight immediately before pregnancy
- Weight prior to delivery
- Age at delivery
- Gestational age at delivery
- Race/ethnicity
- Marital status
- Education level
- Family income
- Use of insulin in pregnancy
- Contraceptive use/type
- Gravidity and parity
- Breast feeding exclusively (yes or no)
- Bottle feeding exclusively (yes or no)
- Mixed breast and formula – how many bottles of formula/day
- Breast feeding exclusively duration
- Mixed breast and bottle duration
- Weight at 3 months and 9 months (groups 2 and 3) and 1 year +/- 3 months (all 3 groups)
- 6 week glucose tolerance test results
- 1 year glucose tolerance test results
- Barriers to adherence—healthy eating and physical activity (from questionnaire)
- Partner support
- self-care and –efficacy,
- perception of infant care giving needs,
- knowledge and fear of diabetes diagnosis,
- depressive symptoms (Edinburgh Postpartum Depressive Scale)
- satisfaction with medical care
- self-report of physician referral for postpartum diabetes screening
- History of other pregnancy complications

The co-investigators will not receive the PHI-containing dataset.

Please answer the following questions:

- Will medical history/clinical information be obtained from the subjects' medical records for the purpose of this study? If yes, please list what information will be recorded.

Approved by
JDC/ CHS
CHS#2012-16

YES

- Height
- Weight immediately before pregnancy
- Weight prior to delivery
- Age at delivery
- Gestational age at delivery
- Race/ethnicity
- Use of insulin in pregnancy
- Contraceptive use/type
- Gravidity and parity

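### Aim 3's weight ANOVA names no analysis variable, time point or baseline term, although the outcome is weight relative to pre-pregnancy weight

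*Combined protocol and SAP*

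**What the plan says.** The whole analysis of Aim 3 in Section 4 is one sentence: "Similarly, for aim 3, we will evaluate the association between our intervention and continuous weight measurements using ANOVA". It does not say which weight, at what time, or whether as a level or a change. Section 2 has women report current weight on every questionnaire, so several weights per woman will exist. The only covariate adjustment in Section 4 belongs to the secondary regression on screening adherence.

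Other parts of the document bear on the point:

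- Section 1, Outcomes, item 3 defines the outcome against a baseline: "Postpartum weight loss (target 7% less than the pre-pregnancy weight for overweight/obese women and back to pre-pregnancy weight for normal BMI women". On the data it says: "This will be based on medical record information on pre-pregnancy weight and self-reported or health-care provider reported weight at 12 months".
- Section 1, Aim 3 asks whether women "will meet postpartum weight goals at 12 months postpartum", again judged against pre-pregnancy weight.
- Section 9 lists "Weight immediately before pregnancy" among the medical-record items sent for analysis.
- Section 3 admits "Preconception BMI 19-40".
- Section 2 gives the size: "we will recruit a total of n=30 women (10 women in each group".
- Section 8 says "Block randomization will ensure an equal distribution of women into each arm". That concerns numbers per arm; no stratification by weight or BMI is stated.

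**The concern.** The outcome is a comparison of each woman with her own pre-pregnancy weight, but the analysis sentence does not mention that weight. Taken at its words, it compares mean measured weight between arms. All the variation in body size that existed before randomisation then goes into the error term. An arm that happened to be lighter before pregnancy would look as if it had lost weight.

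This matters even in a pilot. Section 4 concedes limited power but intends to use the direction and size of the associations to plan a larger study. Chance imbalance between small arms can distort exactly those two things.

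Under a more generous reading, the variable is simply not fixed. The choice between level and change, and between time points, could then be made after the data are seen.

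**Working it through.** The plan gives no SD, effect size or power for weight, so there is no stated figure to reproduce. What follows is an illustration under declared assumptions.

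**From the documents:** 10 women per arm, three arms (Section 2); BMI 19-40 (Section 3); a 7% target for overweight or obese women (Section 1).

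**Assumed:** two-sided alpha 0.05; all 30 women have a 12-month weight; height 1.63 m; pre-pregnancy SD (SDpre) 12-16 kg; SD of individual change to 12 months (SDchg) 5-8 kg, independent of pre-pregnancy weight. As a check on SDpre, 19 × 1.63² = 50.5 kg and 40 × 1.63² = 106.3 kg. An even spread over that range has SD (106.3 − 50.5)/√12 = 16.1 kg, and range/4 gives 13.9 kg.

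**Step 1. SD of measured 12-month weight and implied correlation.** SDraw = √(SDpre² + SDchg²) and r = SDpre/SDraw.

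- (12, 5): √(144 + 25) = 13.0 kg, r = 0.92
- (14, 6): √(196 + 36) = 15.2 kg, r = 0.92
- (16, 8): √(256 + 64) = 17.9 kg, r = 0.89

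The corner cases (12, 8) and (16, 5) give r = 0.83 and 0.95. The ratio of raw to adjusted residual variance, SDraw²/SDchg², runs from 208/64 = 3.2 to 281/25 = 11.2.

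**Step 2. 95% CI half-width for a two-arm difference.**

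- Measured weight, no covariate: t(27) × SDraw × √(2/10) = 2.052 × 13.0 × 0.447 = 11.9 kg, up to 2.052 × 17.9 × 0.447 = 16.4 kg.
- With pre-pregnancy weight as covariate: t(26) × SDchg × √(2/10) = 2.056 × 5 × 0.447 = 4.6 kg, up to 2.056 × 8 × 0.447 = 7.4 kg. A small allowance for estimating the covariate slope makes this 4.7-7.5 kg.
- Plain ANOVA on change: t(27) × SDchg × √(2/10) = 4.6-7.3 kg.

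**Step 3. Chance baseline imbalance.** The difference between two arms in mean pre-pregnancy weight has SD SDpre × √(2/10) = 5.4-7.2 kg. As a yardstick, take 7% of 80 kg = 5.6 kg. The probability that two arms differ by more than this before any intervention is 2 × [1 − Φ(5.6/5.4)] = 0.30, up to 2 × [1 − Φ(5.6/7.2)] = 0.43.

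**Step 4. Power of the three-group F test** for true means 0, −2.8 and −5.6 kg. The noncentrality is 10 × (2.8² + 0 + 2.8²)/SD² = 156.8/SD². For (SDpre, SDchg) = (12, 5), (14, 6), (16, 8):

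- measured weight: 12%, 10%, 8%
- ANCOVA: 55%, 40%, 24%
- ANOVA on change: 55%, 41%, 24%

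**Step 5. Dependence on the correlation.** Here the 12-month SD is set to 14 kg, the effect to 5.25 kg (7% of 75 kg), and the test is pairwise at 10 per arm. The ANCOVA SD is 14√(1 − r²) and the change-score SD is 14√(2(1 − r)). Unadjusted, power is 12.5% and the half-width 13.2 kg.

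| r | ANCOVA power (half-width) | Change-score power (half-width) |
|---|---|---|
| 0.5 | 15% (11.4 kg) | 12.5% (13.2 kg) |
| 0.8 | 26% (7.9 kg) | 24% (8.3 kg) |
| 0.9 | 44% (5.8 kg) | 43% (5.9 kg) |
| 0.95 | 72% (4.1 kg) | 71% (4.2 kg) |

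**The case against.** The strongest reply is that nowhere does the plan say raw 12-month weight will be analysed. Outcome 3 is headed as weight loss and is built from pre-pregnancy and 12-month weight together, so the Aim 3 sentence can be read as ANOVA on change. Steps 2 and 4 show that this already has the precision and power of ANCOVA, and baseline imbalance then largely cancels. This stands. A reader might infer that the plan has committed to the wrong comparison, but the documents do not support that. They leave the variable open. In favour of the literal reading, the sentence is introduced as parallel to Aim 2, which analyses glucose levels and not changes.

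A reader might also infer that differences in body size would drown any intervention effect. That is too strong. It depends on SDs and a correlation that the documents do not give. At r near 0.5 adjustment gains almost nothing, and at r = 0.8 power stays low even after it. The 5.6 kg yardstick is also generous as an arm-level effect, because the 7% target applies only at BMI 25 or above.

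Finally, the plan already discloses limited power. That takes weight from the power contrast, but not from the effect of imbalance on the direction and size of the estimates.

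**Conclusion.** The point holds as a gap in specification with a conditional cost. Section 4 does not fix the variable, the time point or any baseline term for Aim 3, although the outcome is defined against a pre-pregnancy weight that the analysts will hold.

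If measured 12-month weight is analysed, the result does not estimate the stated outcome. Under the assumed SDs (implied correlation about 0.83-0.95), intervals are roughly two to three times as wide as they need be, and a baseline gap larger than 5.6 kg between two arms has a 30-43% chance. If change from pre-pregnancy weight was meant, most of that loss is absent and what remains is the need to say so. Missing 12-month weights would widen every interval shown.

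**What to change.** In Section 4, replace the Aim 3 sentence with one stating that weight at 12 months (+/- 3 months), or percent change from pre-pregnancy weight, will be analysed by ANCOVA on randomised group with pre-pregnancy weight as covariate. Report adjusted mean differences of Groups 2 and 3 versus Group 1 with 95% CIs. ANOVA on change from pre-pregnancy weight would be an adequate alternative, provided it is named in advance.

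The cost is one sentence, one covariate in the SAS model and one residual degree of freedom (27 to 26). No new data are needed: pre-pregnancy weight precedes randomisation and is already on the Section 9 list.

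### Aim 3 has neither BMI stratification nor a baseline term, so chance differences in pre-pregnancy weight add avoidable noise with 10 women per arm

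*Combined protocol and SAP*

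**What the plan says.** - **Goal.** Section 1, Outcomes, item 3 sets two targets: "target 7% less than the pre-pregnancy weight for overweight/obese women and back to pre-pregnancy weight for normal BMI women". Aim 3 puts the cut at 25: the 7% loss applies if "they have a BMI ≥ 25 or return to their pre-pregnancy weight if their BMI < 25".
- **Eligibility.** Section 3 admits "Preconception BMI 19-40", so both goal classes can enrol and the class is known before assignment.
- **Size.** Section 2, Study Population: "we will recruit a total of n=30 women (10 women in each group").
- **Randomisation.** Section 8: "At this time, we will use block randomization, using a random number generator to assign women into one of the three study groups". Its stated purpose is equal numbers: "Block randomization will ensure an equal distribution of women into each arm". No stratification factor or block size is given.
- **Analysis.** Section 4, for Aim 3: "we will evaluate the association between our intervention and continuous weight measurements using ANOVA". No covariate is named. The adjusted regression in that section is for screening adherence, not weight.
- **Data.** Section 9 lists height and weight immediately before pregnancy among the items sent to the analysts.
- **Use.** Section 4 concedes limited power and says that the direction and size of the associations will inform a larger study.

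**The concern.** A woman's 12-month weight depends heavily on what she weighed before pregnancy, and her goal depends on that weight and on her BMI class. With 10 women per arm, chance alone will often leave the arms different on both. An unadjusted comparison of mean weight then carries those starting differences into the estimate. The pilot's product is the estimate rather than a significance test, so noise of this kind matters even though low power is admitted. It is avoidable, because the baseline values are already in the analysis dataset.

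**Working it through.** **Plan's own figure.** 3 arms x 10 = 30 women. No alpha, power or effect size is stated, so nothing further can be reproduced.

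**1. How often BMI class is unbalanced.** Let p be the share with BMI of 25 or more. The documents do not give it. I take 0.50 to 0.714 as an assumption; the upper end is an even spread over the eligible range, (40 - 25)/(40 - 19) = 15/21. Counts per arm are treated as independent Binomial(10, p) and enumerated exactly.

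| p | One given pair differs by 3 or more | Some pair of the three does |
|---|---|---|
| 0.50 | 26% | 50% |
| 0.60 | 25% | 49% |
| 0.714 | 21% | 42% |

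At p = 0.8 the figures fall to 16% and 33%. Fixing the total with BMI of 25 or more at 9 to 21 of 30 gives 40-47% for some pair. Simulated unstratified blocks of 3 and 6, at p = 0.3 to 0.7, give 42-50%.

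**2. What a gap of 3 in 10 does to mean weight.** Two assumed BMI spreads: uniform on 19-40, and normal (mean 28, SD 5) limited to 19-40. The two BMI classes then differ on average by 10.5 and 7.5 units. At an assumed height of 1.63 m (squared, 2.657):
- Uniform: 10.5 x 2.657 = 27.9 kg; 0.3 x 27.9 = 8.4 kg.
- Normal: 7.5 x 2.657 = 19.9 kg; 0.3 x 19.9 = 6.0 kg.

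For scale, 7% of the weight at BMI 28 is 0.07 x 28 x 2.657 = 5.2 kg.

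**3. How much a baseline term removes.** Take 12-month weight as pre-pregnancy weight plus an independent change with SD 5 or 10 kg (assumed). Let height vary with SD 6.5 cm around 1.63 m (assumed). Simulated variance of pre-pregnancy weight: 300.8 kg² (uniform) and 177.0 kg² (normal). The share explained by pre-pregnancy weight is V/(V + SD²):
- Highest: 300.8/(300.8 + 25) = 92%.
- Lowest: 177.0/(177.0 + 100) = 64%.

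BMI class alone explains 49% and 27% in the same two settings.

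The standard error of a two-arm difference in mean weight is √(2 x variance/10):
- Uniform, SD 5: √(2 x 325.8/10) = 8.1 kg unadjusted; √(2 x 25/10) = 2.2 kg with pre-pregnancy weight in the model.
- Normal, SD 10: √(2 x 277.0/10) = 7.4 kg unadjusted; √(2 x 100/10) = 4.5 kg adjusted.

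These ignore the small loss from estimating the slope.

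**4. The same question for goal attainment.** Assume 50% attain the goal below BMI 25 and 20% at or above it. A 3-woman gap shifts expected attainment by 0.3 x (0.50 - 0.20) = 9 points.
- At p = 0.5, overall attainment is 35% and the two-arm standard error is √(2 x 0.35 x 0.65/10) = 21.3 points. With BMI class balanced, the mean within-class variance is 0.5 x 0.25 + 0.5 x 0.16 = 0.205, and the error is √(2 x 0.205/10) = 20.2 points.
- At p = 0.714, the same steps give 20.2 and 19.3 points.

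**The case against.** The strongest reply has four parts.

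- **The randomisation is valid.** Unstratified blocking gives unbiased comparisons, and the sentence on equal distribution claims only equal numbers, which is right. This stands. A reader might infer that missing stratification biases Aim 3; the documents do not support that.
- **For goal attainment the gain is slight.** A reader might take the 9-point shift as a serious distortion. It rests on assumed rates, is under half of one standard error, and concerns a proportion that Section 4 does not plan to analyse. Balancing BMI class would lower the error by about 1 point. This stands: for attainment, 10 women per arm is the main source of noise.
- **The ANOVA may be meant for weight change.** Outcome 3 speaks of weight loss against pre-pregnancy weight. If change is analysed, subtraction already removes most of the baseline variation, and under the simple model above a covariate would add little. But Section 4 says only continuous weight measurements, so the text leaves the raw-weight reading open.
- **Restratifying may come late.** Eligible deliveries run from June 2012 and the approval stamp is dated 03/10/2014. The documents do not say how many women had been enrolled. This is a reason to put the remedy in the analysis.

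A reader might also infer that staff can foresee assignments at the end of a block. No block size or list-holder is stated, so any guess rate would rest on assumed sizes. That is a separate matter of missing detail, not part of this point.

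**Conclusion.** The point holds as a minor, inexpensive improvement. As written, Aim 3 ignores baseline weight and BMI class in both allocation and analysis, although the goal is defined by them. For a given comparison of two arms, a gap of at least 3 of 10 in BMI class arises in about a fifth to a quarter of trials; the 42-50% figure applies to any of the three pairs. The benefit of adjustment is large if raw 12-month weight is analysed and small if change is analysed. All sizes depend on the assumed share with BMI of 25 or more, the assumed BMI and height spreads, and a weight-change SD of 5-10 kg that is independent of baseline. That the 7% goal is the harder one is plausible but also assumed. Aim 1 is unaffected, since screening adherence is not defined by BMI.

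**What to change.** In Section 4, replace the unadjusted ANOVA for Aim 3 with an ANCOVA of 12-month weight, or of percent change from pre-pregnancy weight, with study group as factor and pre-pregnancy weight as covariate. State which of the two outcomes is used. Report arm differences with 95% confidence intervals. Add goal attainment by arm, adjusted for BMI class (<25, >=25) or shown split by it, so that the outcome defined in Section 1 is also reported.

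Pre-pregnancy weight is the better covariate for continuous weight; BMI class belongs with the attainment goal.

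Cost: one or two degrees of freedom (27 residual with all 30 women, falling to 26 or 25), a few sentences, and no new data.

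Optional: stratify the remaining block randomisation by BMI class. If applied from the first enrolment, simulation (p = 0.3 to 0.7) gives a gap in BMI class of at most 1 woman with blocks of 3 and at most 2 with blocks of 6. The downside is slightly unequal arms: sizes differ by 2 in about 45% of runs with blocks of 3, and by up to 4 with blocks of 6. If enrolment is complete, the analysis change alone suffices.

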- Weight at 3 months and 9 months (groups 2 and 3) and 1 year +/- 3 months (all 3 groups)
- 6 week glucose tolerance test results
- 1 year glucose tolerance test results

- Will information resulting from this study (i.e. results of clinical/research lab tests, etc...) become part of the subjects' medical record or provided to the subject and/or others for clinical purposes? If, no, please list what information will not be given to the subject or recorded in their medical record and why.

NO

- Will subjects' identifiable health information* be shared with others outside of Joslin Diabetes Center? If yes, list whom this information will be shared with (please be specific, include names of collaborators, study sponsor contacts)?

NO

10. OMIT PROCEDURES / LEAVE STUDY:

A subject who wishes to leave the study or not participate in any specific study procedures can inform CITI-certified, IRB-approved study staff at any time. Study participants will be given information, as to how to contact study staff or the Principal Investigator of the study. Written or verbal dissent will be accepted and a note will be included in the study participants file to ensure that all study staff are aware of participants' decision.

11. INCENTIVES / REMUNERATION:

Subjects in group 1 and 2 will receive \$50 for completion of the study while subjects in group 3 will receive additional \$50 for reporting their self- glucose tests done through 3 months- 9 months. If a participant only completes part of the study then the remuneration will be prorated. In addition, those who are randomized to the nutrition/exercise classes will receive reimbursement for parking.

12 months (Groups 1, and 2)	\$50.00 check for completion of study
12 months (Group 3)	\$100.00 check for completion of study

* **Identifiable Health Information**

Approved by
IDC/ CHS
CHS#2012-16

[Signature]

Data that includes any of the following identifiers are considered identifiable health information: ("X" denotes data to be collected)

- Name
- Social Security number
- Medical Record Number
- Address by Street Location
- Address by Town/City/Zip Code
- Date of Birth
- Telephone Number
- Electronic E-Mail Address

Approved by
JDC/ CHS
CHS#2012-16

Please answer the following questions:

Where and how will your project utilize the Joslin Diabetes Center?

General Clinical Research Center (GCRC)
 Clinical Trials Unit (CTU)
 Joslin Clinic
 Eye Unit
 Other (please specify) _____

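### Group 3's extra $50 for block glucose tests is folded into a $100 completion check at 12 months; with no proration schedule, the pay that depends on the 12-month contact may be up to twice that of Groups 1 and 2

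*Combined protocol and SAP*

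**What the plan says.** Section 11 sets the payments in three parts.

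- **Sentence.** Groups 1 and 2 are paid $50 for finishing the study, "while subjects in group 3 will receive additional" $50, the latter "for reporting their self- glucose tests done through 3 months- 9 months".
- **Proration.** "If a participant only completes part of the study then the remuneration will be prorated". The shares are not given.
- **Table.** There is one row for Groups 1 and 2 and another that begins "12 months (Group 3". Both are dated 12 months. The amounts are $50 and $100, and each is described as a "check for completion of study". No row covers the block tests.

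The first outcome in Section 1 is "Adherence to diabetes screening using the 75 gram 2 hour OGTT or fasting blood glucose at 12 months", with a window of 3 months either side. Section 2 (Questionnaire to Assess Barriers to Follow-up) says adherence is assessed by asking the woman. Section 2 (Laboratory Data) seeks results from the ordering physician only after she reports a test and returns a signed release. Weight at 12 months may be self-reported or come from a provider.

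Section 4 analyses Aim 1 through "the proportion of women who received postpartum diabetes screening in each group using intention-to-treat analysis" and a chi-square test. It has no rule for women who give no 12-month answer. Aim 1 expects Group 3 to do best, Section 8 says women are not blinded, and Section 2 plans 10 women per group.

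**The concern.** By the sentence, the second $50 is earned by month 9. By the table, it arrives at month 12 as part of a completion payment. A Group 3 woman reading the table could conclude that $100 depends on her last contact, while a woman in Group 1 or 2 would see $50.

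That contact is where the main outcome is collected. If the larger check draws more replies in Group 3, more of its screened women are counted as screened, although no more were tested. The error would favour the group expected to do best. Section 4 accepts limited power and relies on the direction and size of the associations to plan a larger study, so a difference produced by response alone would feed into that use.

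**Working it through.** **1. The plan's own total.** Section 11 gives a base of $50 and an addition of $50. $50 + $50 = $100, which matches the table. Sentence and table agree on the amount and differ on what the second $50 is paid for.

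**2. Pay that depends on the 12-month contact.** The documents supply four questionnaire contacts in every group (6 weeks to 3 months, then 6, 9 and 12 months), two online classes in Groups 2 and 3, and monthly blocks from month 3 to month 9 in Group 3 (7 blocks if both end months count). The proration rules below are assumptions, because the plan states none.

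| Reading | Group 1 | Group 3 | Ratio, Group 3 / Group 1 |
|---|---|---|---|
| (a) Whole check depends on completion, no proration | $50 | $100 | 2.0 |
| (b) Whole check prorated over 4 questionnaires | 50/4 = $12.50 | 100/4 = $25 | 2.0 |
| (c) Extra $50 earned by blocks alone; base paid whole | $50 | $50 | 1.0 |
| (c′) As (c), base prorated over 4 questionnaires | 50/4 = $12.50 | 50/4 = $12.50 | 1.0 |
| (d) Prorated by count of all tasks | 50/4 = $12.50 | 100/(4 + 2 + 7) = $7.69 | 0.62 |

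The ratio runs from about 0.6 to 2.0. Twofold is the upper end, and Section 11 does not say which reading governs.

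**3. What unequal response would do to Aim 1.** Let *s* be the true proportion screened, the same in both groups, and *r* the 12-month response. If non-responders count as not screened and response is unrelated to screening, the observed proportion is *s* × *r*. The values of *s* and *r* are assumed; the documents give none.

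- *s* = 0.50, response 90% against 70%: 0.50 × 0.90 = 0.45 and 0.50 × 0.70 = 0.35. The false difference is 0.10, and 0.10 × 10 women = 1 woman.
- *s* = 0.50, response 90% against 80%: 0.45 − 0.40 = 0.05, or half a woman on average.
- Equal response: no difference.

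**4. Dependence on the counting rule.** If the proportion is taken among responders only, the first case gives 0.45/0.90 = 0.50 and 0.35/0.70 = 0.50, and the false difference disappears. That holds only while response is unrelated to screening.

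**The case against.** The strongest objection is that a reader might infer from the table that the incentive to supply the outcome is twice as large in Group 3. The documents do not fix that figure. The sentence attaches the extra $50 to block-test reports, and the next sentence prorates payment. Read together, they allow a woman who returned her blocks but missed month 12 to keep that $50, leaving the 12-month pay equal. One check can cover two separately earned amounts, so the table may be only a loosely labelled total. This stands, and it limits the claim to a possible inequality of up to twofold.

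A reader might also infer that Group 3 women are paid more to be screened. They are not: screening is optional and no payment is attached to a test. Any bias must run through response.

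Ascertainment does not rest on response alone. Section 9 lists one-year glucose tolerance results and one-year weight among data taken from medical records. That would recover some outcomes and shrink the effect. It is incomplete protection: the list does not name the fasting glucose test, which also counts as screening, and results from outside physicians need the woman's report and release.

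Finally, Group 3 also receives reminders, follow-up letters and telephone calls about block testing (Section 2, Block Blood Glucose Monitoring). These may raise its 12-month response whenever the check is sent. That is true, and changing the payment date will not remove it. It does not justify keeping an avoidable difference in pay.

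**Conclusion.** The point holds in limited form. Section 11 ties the second $50 to work finished by month 9 but schedules it in a 12-month completion check, and the undefined proration leaves open whether the final contact carries equal pay in the three groups. The Group 3 to Group 1 ratio could be 2.0, 1.0 or lower.

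The resulting risk to Aim 1 is plausible and avoidable, but its size is unknown. The 10-point example rests wholly on an assumed 50% screening rate, assumed response of 90% and 70%, and an assumed rule that non-responders count as not screened. Nothing in the documents shows that $50 would produce such a gap, so the example should not be read as an expected bias. Paying the group with more to do a larger total is reasonable and is not criticised here. The change is worth making because it is cheap and keeps that compensation.

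**What to change.** In Section 11:

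1. Pay Group 3's additional $50 after the 9-month block, prorated by blocks returned and not conditional on the 12-month contact.
2. Make the 12-month payment the same in all three groups, with the same written proration. Spreading the $50 base over the four questionnaires common to every group would give 50/4 = $12.50 per contact.
3. Give the block-test payment its own row in the table, so that the table matches the sentence.

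In Section 4, report 12-month response by arm and state how a woman with no 12-month answer enters the intention-to-treat proportion.

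The maximum payment stays at $100 in Group 3 and $50 in Groups 1 and 2. The cost is one extra check for about 10 women and a short amendment. Group 3 may lose some pull towards month 12 compared with a $100 final check, but the pull from payment would then be equal across groups. Other differences in contact, such as the block-testing reminders, remain, so response by arm is still needed to interpret Aim 1.
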